8. ASSOCIATED/ PROHIBITED TREATMENTS AND PROCEDURES

Our aim in this research project is to compare the cost-effectiveness of 2 surgical procedures in the real life practice. Therefore there will not be any prohibited treatment but we will systematically collect the use of any medication that could interfere with the assessment of the primary or secondary evaluation criteria. In particular we will systematically collect the use of any medication related with lower urinary tract symptoms.

9. STUDY PROCEDURE

9.1. STUDY CALENDAR

Duration of the inclusion period: 32 months

• Participation duration of each participant: 12 months

• Total duration of the research: 44 months

• Follow-up in the SNDS database: 3 years

History in the SNDS database: 2 years

9.2. SUMMARY TABLE OF ASSESSEMENTS

Assessments carried out as part of the care (C) or specifically for research (R).

rissessments carried out as			V1	V2	V3	V4	V5
	Inclusion	Intervention	Month 1	Month 2	Month 3	Month 4	Month 12
			(+/- 7 days)	(+/- 7 days)	(+/- 7 days)	(+/- 7 days)	(+/- 14 days)
Patient information (R)	✓						
Informed consent (R)	✓						
Verification of eligibility criteria (R)	1						
Medical and surgical history (R)	1						
Drugs whether or not related to BPH (R)	1	✓	1	1	1	1	✓
Recovery after surgery (R)			✓	✓	✓	✓	
Clinical examination (C)	✓					✓	✓
Biological examination ¹ (C)	✓					✓	1
Urinary flowmetry (C)	✓					✓	✓
Urinary tract ultrasound (C)	✓						
Urine microscopic examination (C)	1	√					
Functional and quality of life questionnaires ² (R)	1					1	√
Complications and adverse effects (R)		/	1	1	1	1	✓
Cost of hospitalization (R)		√					
Health care consumptions (declared by the patient) (R)			1	1	1	1	

¹Blood sample tests: total PSA and creatinine dosage

9.3. INCLUSION VISIT

9.3.1. COLLECTION OF CONSENT

During the inclusion visit, the investigator will inform the participant and answer all questions regarding the purpose, nature of constraints, foreseeable risks and expected benefits of the research. The investigator will specify the participant's rights in the context of the study and the collection of the individual national healthcare identifier (Numéro d'Inscription au Répertoire, NIR) required to link clinical and economic data to those of the SNDS database. The investigator will also check patients eligibility criteria.

A copy of the information package and the consent form will then be given to the participant by the investigator. After this information session, the participant will be given a period for reflection. If the participant agrees to participate, the participant and the investigator will clearly enter their names and surnames and date and sign the consent form. This must be signed BEFORE ANY CLINICAL OR PARA-CLINICAL EXAMINATION REQUIRED BY THE RESEARCH IS CONDUCTED.

If the participant gives his consent to participate, he and the investigator will clearly write their names and surnames and date and sign two original copies of the consent form.

The copies of the briefing note and the consent form will subsequently be allocated as follows:

- The investigator will give a copy of the briefing note and the signed consent form to the participant.
- The investigator will keep the other original copy (even in the event of a change in the participant's address during the course of the research project) in a safe place that is inaccessible to third parties.

² IPSS, IPSSQ8, IIEF15, MSHQEJD, ISI, ICIQ-UI SF, QoR VAS, EQ-5D-5L, Jenkins sleep scale

BPE ST.

ECOLIFT Version no.6.0 of 31/01/2023

9.3.2. CONDUCTING THE VISIT

The investigator will perform the inclusion visit. The inclusion visit will take place between 1 day and at the most 90 days before the surgery. Prior to any research-related examination, the investigator will collect the participant's free, informed and written consent (or that of his legal representative, if applicable).

Clinical examination: general physical examination, digital rectal examination, abdominal palpation, lumbar percussion

Para-clinical examination: urinary flowmetry, urinary tract ultrasound

Blood sample: PSA and creatinine dosages

Auto-questionnaires: IPSS, IPSSQ8, IIEF15, MSHQEJD, ISI, ICIQ-UI SF, QoR-VAS, EQ-5D-5L, Jenkins sleep scale

9.4. INTERVENTION

The surgical procedure will be performed during hospitalisation in an operating theatre. The micro-costing data will be collected during the time of intervention, on the basis of a micro-costing questionnaire developed by the project team. By the end of hospitalisation for the surgical procedure, participant will be provided with a participant diary/book to self-report of healthcare consumptions (medications, hospitalizations, out-patient visits, radiology and biology exams, not reimbursed treatments ...) and QoR-VAS until Visit 4.

9.5. VISITS 1, 2 AND 3

Visit 1, 2 and 3 will be phone call visits performed by the Clinical Research Assistant.

It will be collected according to participant notification:

- All medication in relation with BPH or with the intervention
- All healthcare consumption between two visits
- The QoR-VAS completed by the participant at home
- Any complication or adverse effect will need to be confirmed by a medical doctor and classified according to the Clavien Dindo classification

9.6. VISIT 4

Visit 4 will be performed at the outpatient clinic by a certified urologist at month 4 (+/- 7 days).

- Participants will undergo urinary flowmetry
- Participants will undergo standard physical examination including digital rectal examination, abdominal palpation and lumbar percussion.
- Participants will complete the following standard questionnaires (part of care):
 - o IPSS score
 - o IPSS Q8
 - o ISI (Incontinence symptom index)
 - o ICIQ-UI SF
 - o MSHQ-Ejd
 - o IIEF15
 - o QoR-VAS
 - o EO-5D-5L
 - o Jenkins sleep scale
- Investigator will collect:
 - o Any adverse effect and complications based on Clavien Dindo classification
 - o All medication in relation with BPH or with the intervention
 - o All healthcare consumptions since visit 3

9.7. VISIT 5

Visit 5 will be performed at the outpatient clinic by a certified urologist at month 12 (+/- 14 days).

- Participants will undergo urinary flowmetry
- Participants will undergo standard physical examination including digital rectal examination, abdominal palpation and lumbar percussion.
- Participants will complete the following standard questionnaires (part of care):
 - o IPSS score
 - o IPSS Q8

- o ISI (Incontinence symptom index)
- o ICIO-UI SF
- o MSHQ-Eid
- o IIEF15
- o QoR-VAS
- o EQ-5D-5L
- o Jenkins sleep scale
- Investigator will collect:
 - o Any adverse effect and complications based on Clavien Dindo classification
 - o All medication in relation with BPH or with the intervention

Visit 5 is the end of study visit for participant.

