1.2. RESEARCH HYPOTHESES AND EXPECTED RESULTS

In real life practice, transurethral surgery implies a general anaesthesia, a long hospital stay and length of surgery. Furthermore, complications and side effects associated with transurethral surgery of the prostate are quite frequent and lead to high healthcare costs. In this context, we assume that costs related to PUL implants and surgery could be covered by a reduction in healthcare expenses related to these transurethral surgery events.

Our hypothesis is that from the French healthcare system point of view, PUL (urolift) is a cost-effective strategy compared to classic transurethral surgery (TURP/laser) for selected patients treated for BOO.

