1.5. EXPECTED BENEFITS

PUL surgery is a mini-invasive alternative to BPH standard surgery, performed under local anaesthesia in a day-care surgical unit, which need less operating time, less use of urinary catheter, and less length of stay. The procedure consists of implanting devices and does not involve resection of prostatic tissue, which should avoid some complications.

BPH standard surgery is associated with a significant amount of post-operative complications, as well as with some persistent side effects such as sexual dysfunction and urinary incontinence. Moreover, those persistent side effects may decrease urinary and sexual comfort, which strongly affect the quality of life.

As the procedure does not involve resection of prostatic tissue, we can expect less bleeding complications.

As we expect less use of urinary catheter, infectious complications should be reduced.

This procedure does not involve risk of urinary sphincter lesion so we can expect at least not worse and probably less urinary incontinence.

For men who maintain regular sexual activity, the procedure should preserve ejaculation.

For the type of patient selected in the clinical trial, we think that PUL surgery could achieve acceptable functional improvements compared to baseline and to those of standard surgery.

If our assumptions are confirmed, PUL surgery could be an efficient alternative to standard surgery, with a reduced time and amount of care and fewer complications, as well as an improvement of the overall long-term quality of life by avoiding persistent side effects.

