3. STUDY OUTCOMES

3.1. PRIMARY OUTCOME

The primary endpoint will be the incremental cost per avoided complication (based on Clavien Dindo classification) of PUL compared to transurethral surgery 4 months after the surgical procedure.

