11.2.3. COST-EFFECTIVENESS CRITERIA

We will assess the cost-effectiveness ratio as following: $\Delta C/\Delta E = (Ceval - Cref)/(Eeval-Eref)$ where

- $\Delta C = \cos t$ differences between both surgery
- ΔE = effectiveness differences between both surgery
- Ceval = Cost of PUL surgery
- Cref = Cost of classical surgery (TURP/laser)
- Eeval = Complications observed at 4 months in the PUL group
- Eref = Complications observed at 4 months in the TURP/laser group

The ratio assessment for the second economic criteria (incremental cost/Qalys at 12 months) is the same.

First an unadjusted estimate of the cost-effectiveness ratios will be made. Their 95% confidence interval of the ratio will be estimated by bootstrap. We will then estimate the net monetary benefit of each surgical procedure (BNM = E λ - C), where λ is the differential cost - effectiveness threshold. The distribution of each BNM will be determined by boostrap. This will allow us to develop an acceptability frontier, a curve representing the probability that the BNM of each surgical treatment will be highest for each value of λ between $0 \in$ and $30000 \in$ per avoided complication (or Qaly in the secondary criteria).

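### Minor early complications may be recorded less completely after day-case PUL than during the longer TURP/laser stay, because no contact is planned before month 1 and the diary is not specified to record symptoms

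*Protocol*

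**What the plan says.** **Endpoint.** Section 3.1, with time counted from surgery: "The primary endpoint will be the incremental cost per avoided complication (based on Clavien Dindo classification) of PUL compared to transurethral surgery 4 months after". Section 11.2.3 takes the effect from observed counts: "Eeval = Complications observed at 4 months in the PUL group", and likewise for TURP/laser. Neither section, nor section 4.2, sets a minimum grade, so a self-limiting event counts as much as a serious one.

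**Stay.** Section 1.2 holds that "transurethral surgery implies a general anaesthesia, a long hospital stay and length of surgery". Section 1.5 describes PUL as "performed under local anaesthesia in a day-care surgical unit, which need less operating time, less use of urinary catheter, and less length of stay". Neither gives a number of days.

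**Collection.** The table in section 9.2 ticks complications at the intervention and at every later visit, in both cohorts. The first visit after the intervention is at month 1 (+/- 7 days). Under section 9.5, visits 1 to 3 are telephone calls by a research assistant: "It will be collected according to participant notification". A doctor must confirm and grade what is reported. At month 4 a urologist sees the patient and complications are collected again.

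**Diary.** Section 9.4: "participant will be provided with a participant diary/book to self-report of healthcare consumptions". The examples cover drugs, admissions, consultations, tests and unreimbursed treatments. The recovery scale (QoR-VAS) is added, and the diary runs to visit 4. Complications and symptoms are not listed.

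**The concern.** The way a complication comes to notice changes at discharge, from staff observation to what the patient later reports. Discharge falls at different times after surgery in the two cohorts, so there is a stretch of early post-operative days in which TURP/laser patients are watched and PUL patients are not. An episode of haematuria or difficulty voiding that settles untreated may be charted in the first case. In the second it has to be remembered until a call that may come a week after the one-month point.

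Because untreated events count fully in the primary effect, some of the complications credited as avoided could be complications that were not recorded. Such events cost almost nothing, so losing them alters the denominator of the ratio and hardly touches the numerator. The results are intended to support reimbursement.

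**Working it through.** **1. The Protocol's nearest figure.** Section 11.1 gives a precision of 7% to 11% for proportions of 10% to 50% with 80 patients. Half-width = 1.96 x sqrt(p(1-p)/80): 6.6% at p = 0.10 and 11.0% at p = 0.50. The figures reproduce, but they describe sampling error only and say nothing about detection.

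**2. Who observes the patient, by time from surgery.**

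| Period | PUL | TURP/laser |
|---|---|---|
| Procedure and day-care stay | Staff; collected at the intervention | Staff; collected at the intervention |
| PUL discharge to TURP/laser discharge | Home; diary of care used and QoR-VAS; no planned contact | Staff |
| TURP/laser discharge to month 1 call | Home; same diary; no planned contact | Home; same diary; no planned contact |
| Month 1 to month 4 | Calls, medical confirmation, clinic visit | The same |

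Only the second row differs between cohorts.

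**3. What the difference does.** Suppose both cohorts have the same true frequency p of a given type of complication. Let f be the share falling inside the TURP/laser stay, g the share falling inside the PUL stay (g < f), and s the chance that an event at home is recorded. Take detection in hospital as complete. Then:

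- TURP/laser recorded = p[f + (1-f)s]
- PUL recorded = p[g + (1-g)s]
- Spurious difference in favour of PUL = p(f-g)(1-s)

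The term is zero if the stays cover the same share of events (f = g) or if nothing is lost at home (s = 1); otherwise it is positive. If detection in hospital is h rather than complete, it becomes p(f-g)(h-s), so the direction depends on h being greater than s.

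**4. Which events are exposed.** For events that led to a drug, consultation, test or admission, the diary holds an entry and s should be close to 1, so the term nearly vanishes. It matters only for early events that led to no recorded care.

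**5. Can it be sized?** No.

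- p: section 1.1.2.1 gives 20 to 40%, but for grade 2 and higher. No rate is given for lower grades.
- f and g: no length of stay in days. Section 1.1.2.1 says only that most complications fall within 3 months.
- s: not given.

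**6. A unit of conversion, not an estimate.** If one PUL patient's only complication goes unrecorded, the observed PUL proportion falls by 1/80 = 1.25 points. With effect taken as complications avoided, at the top of the threshold range in section 11.2.3 (30,000 euros) PUL's mean net benefit rises by 30,000/80 = 375 euros per patient.

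**The case against.** The Protocol has real safeguards, and they narrow the point considerably.

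- Detection after PUL is not recall alone. Drug use, visits, tests and admissions go into the diary up to visit 4, so a treated event has a written prompt.
- PUL events on the day of surgery are also collected in hospital, which is why g appears in the formula.
- After discharge both cohorts follow an identical route, and section 14.2 provides for checking the case report form against medical records. The difference is confined to the extra inpatient days, and section 1.1.2.1 says that bipolar and laser surgery have shortened stays.
- The diary form is not among the appendices. The missing complications field is inferred from its description in section 9.4.

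All of this stands. It does not close the gap. Medical confirmation removes false reports but cannot recover an event that was never reported. The month 4 visit asks about the first week later still. Record checks find only what was recorded.

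Two stronger readings are tempting. A reader might infer that under-detection demonstrably favours PUL in the primary effect. The documents show unequal observation, not unequal capture; the direction follows only if staff notice more than patients later report, which is plausible but not stated. A reader might also apply a recall loss to the 20 to 40% rate and obtain a bias in percentage points. That rate is for grade 2 and higher, the events most likely to leave a trace of care, so the result would be anchored to the wrong events.

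**Conclusion.** The point holds in a limited form. The schedule observes the first post-operative days unequally by procedure, the primary effect counts complications of every grade, and nothing described for the interval before month 1 records a minor untreated event at home. Such events may be under-recorded after PUL, which would enlarge the apparent number of complications avoided.

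This assumes that TURP/laser patients stay longer, as sections 1.2 and 1.5 say, that in-hospital detection is better than later self-report, and that the diary contains what section 9.4 describes and no more. No percentage-point range should be quoted. It is a plausible detection bias that is cheap to reduce, and it does not invalidate the design. Whether the statistical analysis plan already contains a suitable sensitivity analysis cannot be seen from the Protocol.

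**What to change.** 1. Add one page to the existing diary in both cohorts for complications and symptoms: date, symptom, and any contact or treatment. Patients complete it from the day of discharge. The research assistant reads it through at each call, with the medical confirmation already planned in section 9.5. If it comes in during recruitment, start it on the same date in both cohorts.
2. Add a sensitivity analysis of the primary ratio restricted to complications of grade 2 or higher, on the assumption that these generally led to treatment and so leave a trace wherever the patient was. If the result changes materially, it depends on minor events and should be read with that in mind.

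The second step needs no new data, because complications are already graded. It remains possible for every patient even if recruitment is too far advanced for the first; this version is dated 31/01/2023 and the summary calendar has inclusion running to Q2 2023.

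The cost is slightly more patient burden and one further analysis, with no additional visit or staff. The restricted analysis will have fewer events and therefore wider intervals, so it should support the primary result and not replace it.

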9.8. SNDS ASSESSMENTS

For each patient identified in the SNDS cohort, the following settings will be defined:

- Inclusion date: date of the surgical procedure completion
- **Look-back period:** 2 years preceding the inclusion date;
- **Follow-up period:** 3 years following the inclusion date.

9.9. RULES FOR STOPPING THE RESEARCH

9.9.1. END OF STUDY

The end of the study corresponds to the end of the participation of the last subject (cf. Articles L.1123-11, R.1123-59 of the Code of Public Health), also called the Last Patient Last Visit (LPLV).

When the study reaches its expected term, the end of the study must be reported to the CPP and ANSM within 90 days.

9.9.2. Premature discontinuation of research

This is particularly the case when the sponsor decides:

- Not to begin the study, despite obtaining the favourable opinion of the CPP to do so.
- Not to resume the research after temporarily discontinuing it or after its suspension by the ANSM.

When the study is definitively discontinued in advance, the end of the study must be reported to the ANSM within 15 days with an explanation of the reasons for doing so.

9.9.3. TEMPORARY DISCONTINUATION OF RESEARCH

The temporary interruption of clinical research (cf. Article R.1123-55 du CSP) consists of:

- Stopping the inclusion of new subjects;
- And/or discontinuation of the medical acts specified in the research protocol.

The ANSM and the CPP must be informed immediately of any decision by the sponsor to end this study. Thereafter, and within a maximum of 15 days following the date of this interruption, an application for authorisation to make substantial modifications to the temporary suspension must be requested from the ANSM and the opinion of the CPP must be sought.

9.10. PROTOCOL DEVIATIONS

Deviations can affect all aspects of a research protocol: inclusion, monitoring, measurement of endpoints, and the treatment process. All deviations must be documented by the investigator and discussed by the steering committee. Even in the event of deviation from the protocol, participants must be monitored until the date planned in the protocol.

9.10.1. Premature and definitive discontinuation of the evaluated treatment

A participant must be considered as stopping the study when he/she no longer follows the study procedure but he/she is still followed in the study (visits, blood samplings...). Everything must be done to collect the information regarding the primary criteria variables in the time lapse expected in the protocol.

Premature discontinuation of the study procedure has to be notified to the coordinating investigator. The reason for, and the date of, the end of the study procedure must be documented. Any patient who stops the study procedure must be cared for as well as possible according to his health status and medical knowledge.

9.10.2. PARTICIPANTS WRONGLY INCLUDED

A participant will be considered wrongly included if all eligibility criteria are not validated. Participants wrongly included should be discussed with the steering committee.

9.10.3. PARTICIPANT LOST TO FOLLOW UP

The coordinating investigator must be informed of any patient lost to follow up.

9.10.4. OTHER DEVIATIONS

Protocol deviations should be documented and justified.

Violations are considered major deviations in:

- regulatory aspects,
- the primary endpoint.

All major violations are subject to a presentation to the steering committee to decide whether the patient's data can be exploited.

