	a description of the associated complications.		
	Comparisons between the PUL and the TURP/Laser cohorts and between the PUL and the SNDS cohorts will be performed after 1 year and 3 years of follow-up in a intention-to-treat analysis using:		
	o a linear regression model when it involves quantitative variables,		
	 a logistic regression model adjusted on potential confounding when it involves qualitative variables. 		
EXPECTED IMPACTS	Results of the study will be used to support French market release, reimbursement, and clinical acceptance of the Urolift system in France.		

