5.1.2. EXCLUSION CRITERIA

- Current urinary retention
- Post void residual urine > 250ml
- Active urinary tract infection at time of treatment

- Previous BPH procedure
- Urethral conditions that may prevent insertion and delivery of device system into bladder (i.e. urethral strictures, meatal stenosis, bladder neck contracture)
- Previous pelvic surgery or irradiation
- History of neurogenic or atonic bladder
- Biopsy of the prostate within the past 6 weeks
- Life expectancy estimated to be less than 1 year
- History of prostate or bladder cancer
- PSA>10ng/ml unless prostate biopsy is negative
- Person intending to move abroad within 1 year after inclusion
- Person placed under guardianship or curatorship
- Person participating to another interventional study on benign prostatic hyperplasia during the study

Patients of the PUL and TURP/LASER cohorts will be identified in the SNDS through their NIR national identifier (if possible) or using a probabilistic linkage with age, hospital identifier (FINESS), date of hospitalization for the procedure and ICD-10 discharge diagnosis. Only patients with a 2-year history before the procedure and a 3-year follow-up after the procedure will be analyzed.

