11.2. STATISTICAL METHODS EMPLOYED

11.2.1. GENERALITIES

Statistical analysis will be performed using SAS® software (SAS Institute, latest current version, North Carolina, USA). Qualitative and ordinal variables will be summarized by frequencies and proportions of each modality, taking into account missingness as a modality. Continuous variables will be summarized by size, number of patients with missing data, arithmetic mean, standard deviation, median, interquartile ranges and extreme values. Confidence intervals will be estimated using Normal approximation for quantitative and qualitative relevant parameters, or bootstrapping method for costs when count < 100 patients.

Standardized mean differences (*Rosenbaum*, *Rubin*, 1985) will be estimated to measure the effect size of quantitative and qualitative baseline characteristics between groups (PUL and TURP cohorts, matched patients of PUL and SNDS cohorts).

For confidence intervals, 2-sided confidence level of 95% will be used. For all tests, a 2-sided significance level of 5% will be used:

- Proportions will be compared between two independent groups using Pearson's Chi-2 test (or Fisher's exact test when expected counts are < 5)
- Means will be compared between two independent groups using Student's t-test when normal distribution is followed (or Mann-Whitney's test when normal distribution is not followed)
- Occurrence of events (retreatment, urinary symptoms) will be estimated across time using Kaplan-Meier estimator and compared between groups with logrank test.
- Adjusted comparisons between PUL and the TURP/Laser cohorts and between PUL and SNDS cohorts will be
 performed in intention-to-treat analysis using linear regression model when it involves quantitative variables,
 and using logistic regression model adjusted on potential confounders when it involves qualitative variables.

[figure not shown]
A Statistical Analysis Plan (SAP) will be developed and will be validated before the analyses.

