11.2.4. SECONDARY CRITERIA

The following analyses will be performed for each cohort, according to the matched treatment group:

- An estimation of the total hospital cost of each surgery procedure based on a top down micro-costing method performed during hospitalization stay;
- A description of the overall and specific urogenital healthcare consumptions during the 3 years of follow-up;
- A description of BPH re-treatment over the 3 years of follow-up (number of patients with a new BPH medication, number of patients hospitalized for BPH surgical procedure);
- A description of urinary symptoms (value of the IPSS, ISI, ICIQ-UI SF scores during the 1st year of follow-up and number of patients with hospitalization for urinary infection, for urinary retention, or for urethral stricture during the 3 years of follow-up);
- A description of the quality of life during the 1st year of follow-up using the IPSS-Q8 score, the Jenkins sleep questionnaire, the EQ-5D-5L questionnaire;
- A description of the recovery after surgery using the Quality of Recovery visual analogue score and the time before returning to normal professional activities;
- A description of the sexual side effects during the 1st year of follow-up using the IIEF15 and MSHQ-EjD questionnaire;
- A description of the associated complications (number and types).

[figure not shown]
A detailed analysis plan will be defined and will be validated by the steering committee of the study. Subsequent modifications must be made before the blinding is lifted on the database and will be systematically validated by the Scientific Council.

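### Section 9.10.4 lets the steering committee decide case by case, with no criteria, deadline or masking, whether major violators' data are used, which conflicts with the intention-to-treat comparisons

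*Protocol*

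**What the plan says.** Section 9.10.4 defines major deviations as those touching regulatory aspects or the primary endpoint, and continues: "All major violations are subject to a presentation to the steering committee to decide whether the patient's data can be exploited". Nothing in the section says on what grounds, by when, or with what knowledge of outcome the decision is taken.

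Section 9.10.2 covers ineligible participants and is weaker: "Participants wrongly included should be discussed with the steering committee". It does not say what follows from the discussion.

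Section 11.2.1 states that the adjusted comparisons of PUL with TURP/laser and with the SNDS cohort will be "performed in intention-to-treat analysis using linear regression model when it involves quantitative variables", with logistic regression for qualitative variables. The data-analysis part of the synopsis says the same comparisons are "performed after 1 year and 3 years of follow-up in a intention-to-treat analysis using" those models.

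Section 11.2.3, on the primary cost-effectiveness ratio, begins: "First an unadjusted estimate of the cost-effectiveness ratios will be made". It names no analysis population.

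The only mention of blinding is in section 11.2.4, about changes to the analysis plan: "Subsequent modifications must be made before the blinding is lifted on the database".

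**The concern.** A rule that lets a committee rule patients in or out one at a time, after inclusion, cannot coexist with an intention-to-treat analysis, which keeps patients in their group whatever deviation occurred. The difficulty is greatest for violations of the primary endpoint. That endpoint is built from complications and costs up to month 4, so such violations will mostly come to light while the outcome is accruing.

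The composition and information of the committee add to this. Under section 12.1.1 it includes the project and scientific coordinators, the economist and a sponsor representative. Under section 12.1.3 it is kept informed of results as they become available. If its members know a patient's procedure and complications when they rule on his data, the exclusions can depend on the outcome. The complication and cost differences would then be biased in an unknown direction. The synopsis says the results are meant to support reimbursement, and section 18.1 names the manufacturer as funder, so an open-ended power of exclusion would be an easy point of challenge.

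**Working it through.** **1. The passages side by side.**

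- Section 9.10: participants with a deviation are still followed to the planned date.
- Section 9.10.1: when the study procedure is stopped early, primary-criterion data must still be sought.
- Section 9.10.4: the committee may nevertheless decide that a major violator's data are not used.
- Section 11.2.1 and synopsis: adjusted comparisons are intention-to-treat.
- Section 11.2.3: no population is named for the 4-month ratio, so 9.10.4 is the only rule in the protocol on setting aside endpoint violators there.

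Missing data therefore do not explain the exclusions. The rule collides directly with the adjusted comparisons and meets nothing that overrides it for the primary ratio.

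**2. What the committee could know.** Sections 7.1 and 7.2 describe two visibly different procedures, and section 4.1 describes a cohort study with no masking. The synopsis schedules the primary-endpoint analysis for Q1–Q2 2024, the remaining clinical analysis for Q3–Q4 2024, and the SNDS analyses for 2026 and 2028. With no deadline in 9.10.4, a ruling that affects a later analysis could be made after comparative results exist.

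**3. The plan's own precision figure.** Section 11.1 gives a 95% half-width of 7% to 11% for 80 patients and proportions of 10% to 50%.

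- 1.96 × √(0.10 × 0.90/80) = 6.6%
- 1.96 × √(0.50 × 0.50/80) = 11.0%

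The figure reproduces.

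**4. Hypothetical sensitivity of the complication difference.** Assumed rates are 24/80 = 30% for TURP/laser, inside the 20–40% that section 1.1.2.1 gives for grade 2 and higher, and 16/80 = 20% for PUL, which is purely an assumption. The starting difference is 10.0 points.

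- Remove three PUL patients with complications: 13/77 = 16.9%; difference 30.0 − 16.9 = 13.1 points.
- Remove three TURP/laser patients with complications: 21/77 = 27.3%; difference 27.3 − 20.0 = 7.3 points.

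The half-width at 20% is 1.96 × √(0.20 × 0.80/80) = 8.8 points. The first shift, 3.1 points, is a little over a third of that and comes from three patients.

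**5. Effect on the ratio.** If the cost difference stayed the same, the ratio would be multiplied by 10.0/13.12 = 0.76 in the first case and by 10.0/7.27 = 1.38 in the second. It would not stay the same. If the three removed men have mean cost c and their full cohort has mean cost m, that cohort's mean cost falls by 3(c − m)/77. Section 1.2 says complications are costly, so c probably exceeds m. The documents give no value for c, so the change in the ratio cannot be stated.

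**6. Effect on the error rate.** This is an exact binomial enumeration of the two-sided 5% pooled z-test, which is equivalent to the Pearson test in section 11.2.1. It takes 80 per cohort, equal true rates, and removal of PUL patients with complications only.

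| True rate | None removed | 3 removed | 4 removed |
|---|---|---|---|
| 20% | 5.0% | 9.4% | 12.4% |
| 30% | 5.1% | 7.3% | 9.1% |
| 40% | 4.7% | 6.5% | 7.5% |

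This is a worst-direction pattern. It shows how few exclusions matter and predicts nothing about the committee.

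**The case against.** The strongest reply is that committee review of major deviations is ordinary practice, and that analysis sets belong in the SAP, which section 11.2.1 says will be validated before the analyses. That is fair as far as it goes: an undefined analysis set in a protocol would be no finding. But 9.10.4 is a rule the protocol states. A SAP that kept all patients would contradict it, and one that followed it would contradict the intention-to-treat wording.

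Several stronger readings are tempting, and the documents do not support them.

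- **The committee decides on the data of wrongly included men.** Section 9.10.2 provides only for discussion. The deciding power is in 9.10.4 and reaches such men only if the case is also a major violation.
- **Many men will become ineligible between inclusion and surgery.** One exclusion is indeed judged at surgery ("Active urinary tract infection at time of treatment"), and inclusion may precede surgery by up to 90 days (section 9.3.2). But the table in section 9.2 schedules a urine examination at the intervention as well, and nothing gives a number.
- **The primary ratio is itself declared intention-to-treat.** The label is attached to the adjusted comparisons, at 1 and 3 years in the synopsis. For the 4-month ratio the defect is silence, not contradiction.
- **The committee is unblinded and known outcomes will decide.** No section says so. The statement on available results is general governance wording. Outcome-aware exclusion is something the text allows, not something it prescribes.
- **The blinding sentence in 11.2.4 is a failed safeguard against exclusions.** It governs changes to the analysis plan and was never a safeguard for 9.10.4. Its wording is a separate, editorial matter.

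The objection that the illustration assumes one-sided exclusions also stands, which is why it is labelled hypothetical.

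**Conclusion.** The point holds in a limited form. Section 9.10.4 gives a committee that may know outcomes an unrestricted, case-by-case power over whether major violators' data are used. This is inconsistent with the intention-to-treat comparisons in section 11.2.1 and the synopsis, and nothing in section 11.2.3 shields the primary 4-month ratio from it. Section 9.10.2 is merely incomplete, because it leaves open what follows from the discussion.

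The size of any bias cannot be derived from the documents. The illustration rests on assumed rates, three exclusions, all with complications and all from one cohort; under those assumptions the difference moves by about 3 points in either direction. The effect on the cost per avoided complication is undetermined without the removed patients' costs. The inference that the committee may know outcomes rests on the visible difference between procedures, the lack of any described masking and section 12.1.3. The text should be settled before the primary analysis.

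**What to change.** In sections 9.10.2 and 9.10.4, state that every included patient who undergoes or starts the index procedure stays in the main analyses, including the 4-month ratio, whatever the deviation. The only exceptions are where the law or withdrawn consent forbids use of the data. State also that discussion of a wrongly included man does not remove him. Define the cohort to which each man belongs in advance, with an explicit rule for a man enrolled for one procedure who receives the other. Name this population in section 11.2.3. Men who consent but never start a procedure fall outside this set and should be counted in the flow chart of section 11.2.2.

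Limit the committee to classifying deviations by criteria written beforehand, before database lock for the analysis concerned, and without sight of complications or costs. Its classification then defines a sensitivity set only.

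Separately, in section 11.2.4, replace the reference to lifting the blinding with a requirement that changes be made before database lock; section 14.3 already provides for a lock.

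The cost is protocol and SAP wording plus one sensitivity analysis. No new data are needed, since sections 9.10 and 9.10.1 already keep follow-up going. The downside is that a few ineligible men remain in the main analysis; the sensitivity set shows whether they matter.
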